Patient Determined Disability Steps	Participant chooses one of 9 categories that describes their MS disability level.		X			X		X	X
MS Walking Scale-12	A 12-item self-report survey; measures the impact of MS on walking ability and daily activities over the past 2 weeks.		X	X	X	X	X	X	X
Godin Leisure-Time Exercise Questionnaire	4 questions; 7-day recall of leisure-time physical activity to determine if individual is already exercising at adequate levels.		X			X	X	X	X
Exercise Preparticipation Health Screening	Questionnaire about physical health to determine if medical consent to participate is required.		X						
Expanded Disability Status Scale	A 30-minute multiple item disease-specific instrument that characterizes disability level and determines disability progression in people with MS.			X			X		X
Timed 25 Foot Walk Test	Measure of walking speed; participant will perform twice. Only one trial must be in the eligibility range for inclusion (6 to 180 seconds). The time of both trials will be averaged for the outcome measure. Participants will be ineligible if physically unable to complete trial 2. If the assistive device/orthosis changes from pre- to post training, participants will be tested with the previous device.			X			X		X
6-Minute Walk Test	Measures the distance an individual can walk over a total of six minutes on a hard, flat surface. The goal is for the individual to walk as far as possible in six minutes. The individual can self-pace and rest as needed as they traverse back and forth along a marked walkway. If the assistive device/orthosis changes from pre- to post training, participants can choose device type, or no device at all.			X			X		X
Mini-Mental Status Exam	11-item test of cognitive impairment.			X					
Demographic survey/medication	Age; gender; type and history of MS; race/ethnicity; insurance status; living arrangements.				X	X	X	X	X
Short Assessment of Health Literacy-English (SAHL-E)	SAHL-E contains 18 items to assess an English-speaking adult's ability to read and understand common medical terms and estimate an adult's health literacy level.				X				
Neuro-QOL	A validated outcome measure of quality of life sponsored by the National Institute of Health recommended by the American Academy of Neurology.				X	X	X	X	X
Modified Fatigue Impact Scale-21	A 21-item self-report of the severity of fatigue and its effect on the participant's activities and lifestyle over the past 4 weeks.				X	X	X	X	X

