If a physician instructs a participant to pause exercising, the site research coordinator must obtain medical clearance from the participant's physician before resuming exercise. If the participant's physician does not instruct a participant to stop exercising, the site PI determines whether or not medical clearance after an AE is required.

Site research coordinators will inform the participant's coaches when medical consent has been obtained and the participant is approved to resume exercising.

Figure 3 below provides additional detail regarding how AEs are reported and addressed.

[figure not shown]
[figure not shown]

Figure 3: AE Reporting and Follow up Procedures

DATA ANALYSIS

Data analysis plan

The primary hypothesis is a non-inferiority test of the changes in T25FWT between GEMS-T and GEMS-S. This will be tested using a linear model with site as the stratification factor and an intention to treat approach. The primary analysis will adjust for covariates age, gender and baseline EDSS or PDDS. Further addition of covariates may be examined in sensitivity analyses based on any differences seen on examination of baseline variables between groups. Secondary endpoints include change in 6MWT and EDSS/PDDS. In all endpoints, we are assessing

improvement over baseline values. We will examine the frequency of worsening as a safety comparison. We will also examine the primary endpoint of a 20% improvement in the T25FWT (yes or no) using logistic regression. Further, to characterize the changes over time, we will use linear mixed models to assess the slopes of change for GEMS-S versus GEMS-T groups. We will also examine the relationship between the dose of exercise measured by compliance and the change in the primary and secondary outcomes. These are exploratory outcomes to see if the compliance measures predict the benefits on the outcomes. This information is important for translation and information dissemination to people with MS.

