Protocol Title: Comparative Effectiveness of an Exercise Intervention Delivered via Telerehabilitation and Conventional Mode of Delivery

Statistical Analysis Plan

PI: [name], Ph.D.

Version: 6/17/2022

Sponsor: Patient Centered Outcomes Research Institute (PCORI)

NCT Number: NCT03468868

Data analysis plan

SA1: Compare the extent of change in walking and mobility outcomes, social and vocational participation, and quality of life. The primary hypothesis is a non-inferiority test of the changes in T25FWT between TET and FET. This will be tested using a linear model with site as the stratification factor included using an intention to treat approach (imputation for missing values are discussed below). The primary analysis will adjust for covariates age, gender and baseline EDSS. Further addition of covariates may be examined in sensitivity analyses based on any differences seen on examination of baseline variables between groups. Secondary endpoints include change in 6MWT and EDSS. In all of these endpoints we are looking at improvement over baseline values whereas many MS studies focus on worsening. We will examine the frequency of worsening as a safety comparison. We will also examine the primary endpoint of a 20% improvement in the T25FWT (yes or no) using logistic regression. Further, to characterize the changes over time, we will use linear mixed models to assess the slopes of change for FET versus TET groups. We also will examine the relationship between the dose of exercise measured by compliance and the change in the primary and secondary outcomes. These are exploratory outcomes and will be assessed with no corrections for multiple testing and are important mostly for descriptive analyses to see if the compliance measures indeed predict the benefits on the outcomes as this information is important for translation and information to people with MS.

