SA2: Evaluate and compare the effectiveness between participants randomized to their preferred delivery mode (TET(Choice) or FET (Choice)) and those who are not randomized to their preferred delivery mode (TET or FET). For this aim we will use the same models as the primary but examining and interaction term for Choice and treatment and contrasts will be conducted comparing the four cells. We will assess if the effect of Choice is the same for both treatments. Logistic regression will be used to assess the interaction between choice and adherence and attendance or dropouts. We also will examine time to dropout and/or time until dropout or poor compliance (which will be defined prior to final analyses). We also are interested in examining the intensity or compliance of the intervention to the choice as well as impact on the primary endpoint as noted above.

SA3: Evaluate changes in self-efficacy and adoption of exercise between these groups (TET, FET, TET(Choice), FET(Choice)). Self-efficacy and adoption of exercise are discussed above and use the same models and approach. We will also utilize mediation analyses to understand if the changes induced by exercise are mediated via the changes in self-efficacy. Here we will use the approach by MacKinnon built on Judd and Kenny.⁷⁹⁻⁸⁴ Analyses of the MSWS-12, MFIS, and the NeuroQOL will all be analyzed using regression models similar to the timed walk models above and will utilize the same contrasts for examining choice as well as treatment effects.

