Data linkage plan. Each participant will be assigned a study ID number when randomized to the intervention group by the biostatistician. This will be the only identifier in all databases and systems used in this study. The Shepherd Center will maintain the master file. None of the investigators or staff involved in the assessments will have access to the identifier data, and thus will remain blinded to the assignment for the entire intervention phase.

Sensitivity analyses. Randomization should balance covariates across treatment groups, but this will be checked with frequency and means tables, and chi-square/Fisher exact and F-tests/t-tests respectively. If treatment groups show important imbalances among covariates, then they can be adjusted for using covariates in various types of regression models as we noted above under the primary analyses. As noted briefly in the primary analysis section, per protocol analyses will be used to support the conclusions of the intention to treat analyses. In the intention to treat analyses we must take into account dropouts. For anyone with at least one post randomization timed walk test, we will impute a model based final endpoint to assess change. Key sensitivity analyses will include adjustment for covariates: age, gender, sex and treatment preference at entry. Interaction terms will be used to identify potential impacts of key covariates. In addition, imputation for missing values will be conducted to assess the impact of these lost observations. We note again that rules are in place to deal with the time variables. For other variables (MSWS, MFIS and NeuroQOL, EDSS) will require various forms of imputation for sensitivity analyses. We will use a general approach discussed below for imputation of these secondary endpoints and use per protocol versus ITT for sensitivity analysis. For the major analyses, best case and worst case analyses will be done. Subgroup analyses will attempt to quantify the consistency of the findings amongst subgroups.

Management of missing data

a. Methods to prevent and monitor missing data.

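### The primary model for change in T25FWT leaves out baseline T25FWT, a covariate already measured on everyone that would usually narrow the confidence interval slightly

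*SAP*

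**What the plan says.** The SAP (Data analysis plan, SA1) sets the primary test: "The primary hypothesis is a non-inferiority test of the changes in T25FWT between TET and FET". The model is a linear one: "This will be tested using a linear model with site as the stratification factor included". On covariates it says: "The primary analysis will adjust for covariates age, gender and baseline EDSS". The protocol (Data Analysis, Data analysis plan) has the same list with one alternative: "The primary analysis will adjust for covariates age, gender and baseline EDSS or PDDS".

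Baseline T25FWT is in neither list. It is also missing from the named sensitivity covariates (SAP, Sensitivity analyses): "Key sensitivity analyses will include adjustment for covariates: age, gender, sex and treatment preference at entry". It could come in only through the clauses in SA1 and in Sensitivity analyses that permit extra covariates when baseline differences are seen. Those are optional and leave the primary model as written.

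The variable is available. A T25FWT time in a set range is an inclusion criterion (Protocol, Participants). The test is done twice at Visit 1 and, by Table 1, "The time of both trials will be averaged for the outcome measure". Randomization follows once baseline measures are complete (Protocol, Enrollment).

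Other analyses inherit the choice. For SA2 the SAP states "we will use the same models as the primary". Under SA3, the MSWS-12, MFIS and Neuro-QOL "will all be analyzed using regression models similar to the timed walk models above", which leaves open whether each model contains its own baseline.

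**The concern.** A change score subtracts baseline with a fixed coefficient of 1. If the slope of follow-up on baseline differs from 1, the change still depends on where a participant started. Two things follow when baseline is not in the model.

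- **Chance imbalance moves the estimate.** With a slope below 1, an arm that happens to start slower tends to show more improvement. A slower start in the telerehab arm would then push the result towards non-inferiority, and a faster start would push it away.
- **The interval is wider than necessary.** Variation in change that baseline could explain stays in the residual. A non-inferiority conclusion normally rests on a confidence bound set against a margin, so width and chance shifts both bear on the answer.

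EDSS and age capture part of walking speed, but the direct measure of it is left out. This is a question of precision and conditional accuracy: in the randomized comparison the estimate is unbiased on average either way.

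**Working it through.** **Inputs from the documents.** 400 participants: 200 Choice, who pick their mode, and 200 No Choice, randomized 100:100. Two T25FWT trials are averaged. The eligible range is 6 to 180 s, and one trial in range is enough. Neither document states a margin, alpha, power, SD, baseline/follow-up correlation or expected dropout, so there is no plan figure to reproduce and every size below rests on assumed inputs.

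**Step 1: algebra, no other covariates.** Let s0 and s1 be the baseline and follow-up SDs and ρ their correlation.

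- Residual variance of the change score: s0² + s1² − 2ρ·s0·s1
- With baseline in the model: s1²(1 − ρ²)
- Difference: (s0 − ρ·s1)², which is never negative. It is zero only when the slope of change on baseline is zero.

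With s0 = s1 the interval width ratio is √((1 + ρ)/2), and the change-score estimate moves by ρ − 1 seconds per second of baseline imbalance.

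**Step 2: baseline EDSS already in the model.** Assume EDSS correlates c = 0.5 with both walk times. Replace ρ by the partial correlation (ρ − c²)/(1 − c²).

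| ρ | width ratio, no EDSS | partial correlation | width ratio, EDSS in model |
|---|---|---|---|
| 0.7 | √0.85 = 0.922 | 0.45/0.75 = 0.600 | √0.800 = 0.894 |
| 0.8 | √0.90 = 0.949 | 0.55/0.75 = 0.733 | √0.867 = 0.931 |
| 0.9 | √0.95 = 0.975 | 0.65/0.75 = 0.867 | √0.933 = 0.966 |

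Simulating the planned model (site, age, gender, EDSS) at 100 per arm gave 0.896, 0.933 and 0.969 for the last column.

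**Step 3: unequal SDs (no EDSS).** The gain depends heavily on s1/s0. For ρ = 0.7, 0.8 and 0.9, s1 = 1.2·s0 gives ratios 0.983, 0.9985 and 0.989, which is almost no gain. With s1 = 0.8·s0 they are 0.792, 0.800 and 0.780.

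**Step 4: simulation on the seconds scale with skewed times.** There were 64 input sets with 4,000 trials each, 100 per arm and no true effect. Assumed inputs:

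- median 9 or 12 s; log-SD 0.4 or 0.7
- per-trial noise 10% or 15%; SD of individual change 15% or 25%
- correlation with EDSS 0.5 or 0.7, and with age 0.2
- mean improvement 0% or 10%; seven site groups

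Change was regressed on arm, site, age, gender and EDSS, with and without baseline T25FWT.

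| Quantity | Range | Median |
|---|---|---|
| Variance ratio, with/without | 0.860 to 1.000 | 0.965 |
| Interval width ratio | 0.931 to 0.999 | 0.985 |
| Shift in planned estimate per 1-SD chance imbalance, in SEs | −0.32 to +0.04 | −0.13 |
| Coverage of 95% CI, with baseline | 94.4% to 96.3% | |
| Coverage of 95% CI, without | 94.3% to 96.3% | |

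The variance cut is 0% to 5% with no mean change and 2% to 14% with a 10% mean improvement. It is under 4% in 38 of the 64 sets and under 1% in 10. The planned estimate moves by −0.151 to +0.020 s per second of baseline imbalance. Re-running the same 64 input sets with fresh code gave similar figures, with the dependence on imbalance close to zero once baseline was in the model.

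These gains are smaller than in Step 2 because follow-up-on-baseline slopes here were 0.84 to 1.02, closer to 1. In sample-size terms, the median variance ratio for the 200 randomized to mode is worth 200/0.965 ≈ 207 participants, and the best case 200/0.860 ≈ 233.

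**The case against.** The strongest reply is that the gain is small and its size assumed. A median 1.5% of interval width, unchanged coverage and a median shift of 0.13 SE do not show that the planned analysis is wrong; change scores with and without baseline adjustment are both legitimate in a randomized comparison. That stands, and it is why this is offered as an improvement rather than an error.

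A second reply is that the plan already deals with imbalance, through the optional covariate clauses and the mixed models for slopes. These do not meet the point. The clauses are prompted by the data and none puts baseline T25FWT in the primary model; the mixed models describe change over time and are not the primary test.

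Third, a linear term removes only linear dependence, and walking times may be skewed. This is correct in principle. With log-normal times the residual dependence was at most 0.05 s per second, and coverage held.

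Fourth, the addition is not neutral in the Choice cells, which SA2 analyses with the primary model. Suppose two self-selected groups differ by d at entry, neither changes, and the slope b is below 1 through measurement noise alone. The change score then shows no difference, whereas the adjusted model shows d − b·d = (1 − b)d. Other patterns of change can reverse this. The caution is sound. No benefit is claimed for the self-selected comparison, and the same caution applies to SA1 if its comparison pools Choice and No Choice participants.

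**Conclusion.** The point holds. Both documents omit baseline T25FWT from the primary model and from the named sensitivity covariates, although every randomized participant should have it. Adding it would usually narrow the interval slightly (0% to 7%, median 1.5%, under the Step 4 inputs) and would remove the linear dependence of the estimate on chance imbalance in walking time. The omission is certain. The size of the gain is not: it rests on assumed SDs, correlations and test noise, on complete data, and on the randomized 100:100 comparison, and it can be near zero. This is a worthwhile low-cost improvement; it does not threaten the validity of the primary test.

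**What to change.** In SAP SA1 and in the protocol's Data analysis plan, add baseline T25FWT, defined as the mean of the two Visit 1 trials, to the primary covariates. In both documents add one sentence saying that models for 6MWT, MSWS-12, MFIS, Neuro-QOL and any other change outcome include that outcome's own baseline value. Where a participant could have more than one pre-randomization value (rescreening after the COVID-19 pause; MSWS-12, which Table 1 marks at Screen 2, Visit 1 and Enrollment), say which one counts. For SA2, state that adjusted comparisons involving self-selected participants remain observational.

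The cost is a few lines of text in each document and one degree of freedom per model, with no new data. The documents do not show whether outcome data have been examined. If they have, report the adjusted model alongside the planned one and label it as a later addition.
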